6.7 Pregnancy and Follow-up Visit

Subjects who become pregnant during the conduct of this study will be discontinued from the study. They will return to the NIH CC 4 weeks after

discontinuation of mepolizumab for clinical assessment, including physical examination and safety laboratory tests. They will be entered into the mepolizumab pregnancy registry and followed on 94-I-0079 for their disease and eosinophilic process but will be removed from this protocol and will not receive further doses of mepolizumab on this study.

6.8 Recontact of Subjects After Trial Termination

Subjects will not be recontacted on this study after trial termination. Subjects will remain on the screening protocol 94-I-0079 on which they may be recontacted if there are important findings that result from this study.

7. Study Procedures/Evaluations

7.1 Clinical Evaluations

7.1.1 History and Physical Exam

A complete medical history and physical examination will be performed as part of the enrollment and baseline evaluations. Subsequent clinical evaluations will focus on the assessment of new symptoms, signs, or untoward medical events. Vital signs, including blood pressure, heart rate, and body temperature, will be measured as part of all physical examinations, according to standard nursing practice. Weight will be assessed at all visits. Subjects sometimes have demonstrable changes in sizes of limbs (forearms, upper arms, or legs). As such, limb diameter measurements will be taken at all visits. More specifically, maximal forearm and upper arm diameter of both arms will be taken 2 inches above and below the cubital fossa. Similarly, for lower extremities, maximal diameter will be measured in both legs 3 inches above and below the popliteal fossa in all patients. Other measurements may be taken on an individual subject depending on symptoms.

7.1.2 Photography and Infrared Thermography

Full or partial body photographic documentation of skin and musculoskeletal involvement will be obtained at enrollment (Visit 1), baseline (Visit 2), and Visit 5 as well as if clinically indicated. Infrared thermography may be used to assess extent of skin involvement using a gradation of colors to demonstrate emission of heat, or thermal radiation, emitted from a surface, if available. Subjects will be asked to refrain from eating for 4 hours prior to thermography so pictures can be compared in the future. The room may also be kept cooler than usual (about 22°C or 72°F) during infrared thermography. Images will be analyzed, transmitted, and stored securely to maintain confidentiality and privacy of subjects.

7.1.3 Symptom Logs and Patient-reported Outcomes

Patients will fill out a daily log capturing symptoms, weight, and temperature (Appendix E: Patient Symptom Log), and fill out validated patient-reported outcome measures for angioedema (daily) and quality of life (monthly; questionnaires provided as [Appendix G](#)). These logs and measures will be completed electronically using REDCap. Subjects will also be encouraged to notify the investigators of any new signs or symptoms that develop between study visits. The daily logs and measures will be completed through the end of study endpoint assessments (Visit 8). For subjects in the de-escalation phase, after Visit 8 until study completion, weekly angioedema and monthly quality of life questionnaires will be continued, and weekly symptoms logs ([Appendix F](#)) will be completed.

7.1.4 Optional Bone Marrow Biopsy and Aspiration

Optionally once before starting study treatment or at the time of peak symptoms (Visits 1 or 2), and once while on study drug, subjects may be asked to participate in bone marrow biopsy and aspiration. If bone marrow was already collected at the NIH (e.g., under protocol 94-I-0079), the study team may instead request a portion of that sample for analyses under this protocol.

Bone marrow biopsy and aspiration will be performed using standard sterile techniques. Local anesthesia (lidocaine) will be administered. Any additional anesthetic (e.g., oral benzodiazepine) will be administered at the discretion of the investigator. Each aspirate typically provides 2-3 mL of bone marrow, and 2-10 aspirates will be obtained.

7.1.5 Optional Skin Punch Biopsy

Optionally once before starting study treatment (Visits 1-3) subjects may be asked to undergo skin punch biopsy.

Skin punch biopsy will be performed using standard sterile techniques after administration of local anesthesia (lidocaine). Two to three 3-mm biopsies will be collected for histopathology, transcriptomics, and fibroblast cultures. Punch biopsies will be obtained by credentialed clinicians following standard procedures. One to two sutures will be placed as appropriate.

7.2 Laboratory Evaluations

Routine laboratory evaluations, including CBC with differential, routine chemistries, and urinalysis, will be performed in the Department of Laboratory Medicine at the NIH CC or at outside laboratories. Serum, plasma, whole blood, and urine will be collected at various timepoints for assessment of eosinophil activation, cytokine/chemokine profile, and other immunologic parameters as described in Appendix H: Research Studies. Bone marrow and skin punch biopsy

samples will be stored for future research, including exploratory research of progenitor cells and fibroblasts, respectively.

7.2.1 Specimen Preparation, Handling and Shipping

Research samples collected at the NIH will be either sent to Clinical Support Laboratory, Frederick National Laboratory for Cancer Research, Leidos Biomedical Research, Inc. for processing or will be transported from phlebotomy to Building 4/B1-28 for processing by laboratory staff after collection. No samples will be shipped to other sites.

8. Potential Risks and Benefits

8.1 Potential Risks

8.1.1 Mepolizumab

The risks of mepolizumab and AE profile have been well described in several prior studies of mepolizumab in asthma, eosinophilic granulomatosis with polyangiitis, and HES. ARs with a $\geq 5\%$ incidence include: headache, injection site reactions (pain, erythema, swelling, itching, burning), back pain, and fatigue. Mepolizumab 100 mg and 300 mg have been approved for SC use. The package insert lists the following risks of mepolizumab use: hypersensitivity reactions including anaphylaxis, angioedema, bronchospasm, hypotension, urticaria, and rash; and herpes zoster infection (12). Other noted findings in studies of mepolizumab include the development of anti-drug antibodies; however, neutralizing antibodies were only identified in 1 of 260 patients with severe asthma receiving mepolizumab 100 mg. Such antibodies are not considered to affect the course of treatment. Additionally, there are unknown risks to the fetus in the case of pregnancy or nursing infants (see section 4.3).

8.1.2 Oral Corticosteroids

Prednisone and other oral corticosteroids are commonly used to treat a wide variety of disorders, including HES. Some subjects enrolled on this study will be on prednisone (or equivalent corticosteroid) for treatment (although subjects could be enrolled off all background therapy). Although the protocol does not administer corticosteroids specifically, the subjects will be required to maintain their current therapy throughout the duration of the protocol without further attempts to taper to ensure that changes in counts and cycles are not a result of alteration of therapy. As such, the risks of continuing on corticosteroids are listed here. The common side effects of corticosteroids are well described and include increased appetite, insomnia, fluid retention, indigestion, headache, facial swelling, menstrual irregularities, and visual changes. When used over extended periods of time, corticosteroids may cause weight gain, cataracts, myopathy, osteoporosis, glucose intolerance, increased risk of infections such as *Pneumocystis jirovecii*, and can affect mood. Subjects will be monitored closely

for these side effects as per usual care. Additionally, evidence-based approaches for glucocorticoid bone loss prevention or treatment will be followed.

8.1.3 Optional Bone Marrow Biopsy and Aspiration

Bone marrow biopsy and aspiration is optional in this protocol. It is a common medical procedure associated with low risk. Risks include the potential for bleeding and a small possibility of infection at the aspirate site that may require antibiotic treatment. There is usually some pressure-like discomfort during needle insertion, and the procedure may result in a bruise and/or some discomfort at the biopsy site or surrounding tissue for 1-2 days after the anesthetic wears off. Standard procedures will be followed for all bone marrow biopsies to minimize pain and the possibility of infection.

8.1.4 Optional Skin Punch Biopsy

The risks of skin punch biopsy include local pain, bleeding, infection, and potential scar and keloid formation. Antibiotics and oral analgesics will be used to manage infection and pain, respectively. The local anesthetic may cause skin irritation. These risks should not be substantially different than those experienced with diagnostic biopsies routinely done on inflamed or infected skin. Any nonroutine complications resulting from the procedure will be addressed in consultation with the NIH CC Dermatology service.

8.1.5 Blood Drawing and IV Insertion

The potential risks of IV catheter insertion and the needle stick for blood drawing include pain, fainting, infection and bruising, or a small hematoma. The bruising may last up to 72 hours. Any hematomas will be treated with local pressure. Infection from the needle puncture is rare, but if this does occur, appropriate treatment will be given. The total blood drawn during the study is within the guidelines of the NIH CC (Medical Administrative Policy 95-9, Guidelines for Limits of Blood Drawn for Research Purposes in the Clinical Center: <http://cc-internal.cc.nih.gov/policies/PDF/M95-9.pdf>) (see [Appendix C](#): Blood Volumes for Specimen Collection for total blood draw volumes).

8.1.6 Photography and Infrared Thermography

Taking pictures of the face and body may be embarrassing to some people. Infrared thermography, in contrast, would not risk exposing the patients identity. These photographs may be published in medical journals, without identifying the subject. We will attempt to preserve the anonymity of the subject as much as possible while providing the information needed to support the research being published. Subjects may decline photographs or place any restrictions on their use. Subjects will be given the opportunity to discuss this with the principal or associate investigators.

8.2 Potential Benefits

Since the effect of mepolizumab in EAE is unknown, subjects may or may not benefit from the experimental therapy. Findings from this study will help researchers understand the underlying mechanisms of EAE and possibly identify a new therapeutic option for patients.

9. Research Use of Stored Human Samples, Specimens, and Data

- **Intended Use:** Samples, specimens, and data collected under this protocol may be used to study factors related to etiology of EAE. Blood samples from subjects may be used for genetic analysis, including RNA expression (transcriptomics) and analysis of target variants of interest in EAE by real-time polymerase chain reaction. Genetic analyses will be for research purposes only, and no individual genetic results will be returned to subjects. Screening for diseases unrelated to EAE will not be performed, and findings unrelated to eosinophilia and immune function will not be further investigated. Genetic data will be coded and stored securely as described below. Deidentified genetic data (specifically transcriptomic data) may be shared in public databases as described in section 10. The informed consent document will describe the possible future use of stored specimens and data.
- **Storage:** All of the stored study research samples are labeled by a code that only the investigators can link to the subject. Serum will be stored in a -80°C freezer, cells in liquid nitrogen, and tissue samples at room temperature or frozen as appropriate. Data will be kept in password-protected computers. Only investigators or their designees will have access to the samples and data.
- **Tracking:** Samples and data will be tracked using Biological Specimen Inventory software.
- **Disposition:** In the future, other investigators (both at NIH and outside) may wish to use these samples and/or data for research purposes. If the planned research falls within the category of “human subjects research” on the part of the NIH researchers, NIH IRB review and approval will be obtained. This includes the NIH researchers sending out coded and linked samples or data and getting results that they can link back to their subjects.
- **Loss or Destruction:**
 - Any loss or unanticipated destruction of samples (for example, due to freezer malfunction) or data (for example, misplacing a printout of data with identifiers) that meets the definition of a reportable event will be reported to the NIH IRB according to NIH Human Research Protections Program (HRPP) Policy 801.

- Additionally, subjects may decide at any point not to have their samples stored. In this case, the principal investigator will destroy all known remaining samples and report what was done to both the subject and to the IRB. This decision will not affect the subject's participation in other protocols at NIH.

10. Data Sharing Plan

Human data generated in this study will be shared for future research as follows:

- Identified data in the Biomedical Translational Research Information System (BTRIS)
- De-identified transcriptomic data in a public repository such as the National Center for Biotechnology Information Gene Expression Omnibus or Sequence Read Archive
- De-identified data with approved outside collaborators under appropriate agreements
- De-identified data will be shared with the public at the time of publication and/or public presentations

Data will be shared at the time of publication or shortly thereafter.

If this study and future research using samples and data collected in this study are expected to generate genetic data that triggers the NIH Genomic Data Sharing Policy, which applies to all NIH-funded research that generates large-scale human (e.g., transcriptomic data), the NIH Genomic Data Sharing Policy (<https://osp.od.nih.gov/scientific-sharing/policies/>) will be followed for deposition of data into the appropriate database (e.g., dbGaP).

11. Remuneration Plan for Subjects

Subjects will not be compensated for participation in this study, but will be reimbursed for out-of-pocket expenses related to at-home sample collection and their transportation costs as is permitted by the NIAID travel policy.

If in-person visits are performed remotely due to the COVID-19 pandemic, subjects will be reimbursed for the costs of remote procedures or the costs will be paid directly from study funds (e.g., shipping samples collected remotely).

12. Assessment of Safety

AEs and other reportable events are defined in NIH HRPP Policy 801: Reporting Research Events.

12.1 Toxicity Scale

The investigator will grade the severity of each AE according to the “Common Terminology Criteria for Adverse Events (CTCAE)” (v 5.0), which can be found at: http://ctep.cancer.gov/protocolDevelopment/electronic_applications/ctc.htm

12.2 Recording/Documentation

At each contact with the participant, information regarding AEs will be elicited by appropriate questioning and examinations. All events, both expected/unexpected and related/unrelated will be recorded on a source document. Source documents will include: progress notes, laboratory reports, consult notes, phone call summaries, survey tools, and data collection tools. Source documents will be reviewed in a timely manner by the research team. All reportable AEs that are identified will be recorded in CRIMSON. The start date, the stop date, the severity of each reportable event, and the principal investigator’s judgment of the AE’s relationship and expectedness to the study agent/intervention will also be recorded in CRIMSON.

If a diagnosis is clinically evident (or subsequently determined), the diagnosis rather than the individual signs and symptoms or lab abnormalities will be recorded as the AE.

A laboratory abnormality will not be recorded as an AE if ALL of the following criteria are met:

- It is no more than “Grade 1” or “Mild” per the protocol-specified toxicity table (or investigator assessment if not listed on the table); AND
- It does NOT require an intervention (e.g., discontinuation of treatment, dose reduction/delay, additional assessments, or treatment); AND
- It is assessed by the principal investigator as NOT related to the study agent(s); AND
- It is assessed by the principal investigator as NOT clinically significant (e.g., the abnormal value does NOT suggest a disease or organ toxicity).

Laboratory findings that are known to be associated with the disease under study (EAE) will not be recorded as AEs (e.g., elevated Ig, aldolase, leukocytes such as eosinophils, neutrophils, or lymphocytes, and serum tryptase).

All abnormal laboratory findings will be reviewed on a routine basis by the principal investigator to identify potential safety signals. An abnormal lab not included on the toxicity table should be assessed in a similar fashion to the criteria above.

12.3 Pregnancy

Although pregnancy itself is not an AE, events occurring during pregnancy, delivery, or in the neonate (e.g., congenital anomaly/birth defect) may be AEs or serious AEs (SAEs).

In the event of pregnancy, the following steps will be taken:

- Discontinue the study agent and procedures and withdraw from this study, but continue to follow-up for safety until delivery or termination of the pregnancy on 94-I-0079.
- Enroll in pregnancy registry.
- Report to the IRB.
- Advise research participant to notify the obstetrician of study participation and study agent exposure.

12.4 Type and Duration of the Follow-up of Participants after Adverse Events

AEs that have not resolved by the end of the follow-up period will be followed until final outcome is known. If it is not possible to obtain a final outcome for an AE (e.g., the participant is lost to follow-up), the reason a final outcome could not be obtained will be recorded by the investigator in CRIMSON.

12.5 Pausing Rules for an Individual Participant

Pausing is the suspension of administration of study agent to a single participant until a decision is made whether or not to resume administration of the study agent.

The pausing criteria for a single participant in this study include any of the following:

- A participant experiences an SAE that is unexpected and possibly, probably, or definitely related to a study agent;
- A participant experiences 2 Grade 3 or greater AEs that are unexpected and possibly, probably, or definitely related to a study agent;
- Any safety issue that the site investigator determines should pause administration of a study agent to a single participant.

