For the SC formulation: Mepolizumab administration will occur via an autoinjector and will be given by the subject or a caregiver as multiple injections of 100-mg each. Each injection should be given into the thigh or abdomen (avoiding the 5 cm [2 inches] around the navel) when given by the subject or caregiver; the upper arm may be used if the injection is administered by a caregiver. Each injection site should be separated by at least 5 cm (2 inches). Injections should not be administered into areas of skin that are tender, bruised, red, or hard. If a dose is missed, it should be administered as soon as possible. Thereafter, the subject should resume dosing on the usual day of administration. If the next dose is already due, then it should be administered as planned.

Dose Adjustments/Modifications/Delays

During the Primary Study Phase administering mepolizumab at 700 mg IV, the dose will remain the same without modification unless held or stopped due to a

pause (section 12.5), halt (section 12.6), or withdrawal of the subject (section 12.8). During the Dose De-escalation Phase, the dose will be reduced as outlined in the protocol unless held or stopped due to a pause, halt, or withdrawal of the subject.

Duration of Therapy

A total of 3 doses of 700 mg IV will be given on this protocol over a 3-month duration for all subjects; subjects in the Dose De-escalation Phase will have 6 months of additional de-escalating doses at 500 mg (3 doses) and 300 mg (3 doses). The total duration of therapy for participation in both the Primary Study Phase and the Dose De-escalation Phase will be 9 months.

Tracking of Dose

A record of the number of doses and lots used will be kept in the pharmacy for doses administered in-person at the NIH Clinical Center Day Hospital. For remote visits during the Dose De-escalation Phase, subjects will either have an observed administration via telehealth or will log the dose on a dose tracker.

Limitations on Prior Therapy

Subjects who have received mepolizumab within 6 months or 5 half-lives (whichever is longer) will not be eligible for this protocol.

Use of Ancillary Medications/Over-the-Counter Products/Foods

Only corticosteroids will be permitted for treatment in addition to mepolizumab. There are no restrictions on use of other prescribed medications, over-the-counter products or foods.

Subject Access to Study Agent After End of Study Assessments

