12.5.1 Reporting a Pause

If a pausing criterion is met, a description of the AE(s) or safety issue must be reported by the principal investigator within 1 business day to the IRB by fax or email.

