12.5.2 Resumption of a Paused Participant

The principal investigator will determine whether or not it is safe to resume administration of the study agent to the participant. The principal investigator will notify the IRB of the decision on resumption of the study agent.

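### A related anaphylaxis that the principal investigator classes as expected would mandate neither a pause under 12.5 nor the report under 12.5.1

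*Combined protocol and SAP*

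**What the plan says.** Section 12.5 defines the measure: "Pausing is the suspension of administration of study agent to a single participant until a decision is made whether or not to resume". It then lists three criteria.

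- One serious event: "A participant experiences an SAE that is unexpected and possibly, probably, or definitely related to a study agent".
- Two severe events: "A participant experiences 2 Grade 3 or greater AEs that are unexpected and possibly, probably, or definitely related to a study agent".
- A discretionary criterion with no condition on expectedness, relatedness, grade or count: "Any safety issue that the site investigator determines should pause administration of a study agent to a single participant".

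Section 5.4 makes dosing the default. For the 700 mg phase, "the dose will remain the same without modification unless held or stopped due to a" pause, halt or withdrawal. For de-escalation, "the dose will be reduced as outlined in the protocol unless held or stopped due to a pause, halt, or withdrawal of the subject".

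Section 12.5.1 sets the report to the IRB within one business day: "If a pausing criterion is met, a description of the AE(s) or safety issue must be reported by the principal investigator". Section 12.5.2 covers restarting: "The principal investigator will determine whether or not it is safe to resume administration of the study agent to the participant".

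Three other places bear on how an event is classed. Section 8.1.1 names anaphylaxis among the package-insert risks of mepolizumab. Section 12.2 has the principal investigator judge relationship and expectedness for each reportable event. Section 12 refers to HRPP Policy 801 for the definitions of adverse events; that policy is not among the documents.

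**The concern.** Expectedness is a sensible filter for deciding which events are news to an oversight body. It is a poor filter for deciding whether one person should receive another dose of a drug that has just caused a serious reaction. Because anaphylaxis is a listed risk, classing it as expected is plausible, and that classification removes the event from both event-defined triggers. The rule is then weakest for the serious reaction that is already known.

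At stake is re-exposure of a participant without a mandatory hold and a recorded decision. Some features of the trial add weight. After the infusions at Visits 4 and 8, participants may leave after 30 minutes (6.3.2, 6.4.1). Dosing at Visits 9 to 13 may be remote, with autoinjectors used by the participant or a caregiver, and a remote dose may be logged on a tracker instead of being observed (5.4, 6.4.2, 6.4.3). Urticaria and angioedema are features of EAE (1.1) as well as listed drug reactions (8.1.1), so attribution may take thought.

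**Working it through.** No rate enters this check, because the documents give none for anaphylaxis. The first two steps apply the rules to one case; the third works out how much time a pause would have.

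**Step 1: the criteria in 12.5.** The case is one anaphylaxis, at least possibly related, classed as expected.

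| Criterion | Requires | Met? |
|---|---|---|
| One SAE | unexpected and related | No: not unexpected |
| Two AEs of Grade 3 or higher | unexpected and related, two events | No: not unexpected, and only one event |
| Any safety issue | a decision by the site investigator | Only if the investigator so decides |

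Event-defined criteria: 2. Containing the unexpected condition: 2. Met by this case: 0. If the same event were serious and judged unexpected, the first criterion would be met, so the result depends on the classification.

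**Step 2: is there another mandatory hold or report?**

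- 5.4 holds or stops a dose for a pause, halt or withdrawal.
- 12.6 carries the same unexpected condition in its event-defined rules, needs two or more participants, and leaves the halt to the principal investigator.
- 12.8 requires withdrawal for a clinical AE when continuing is not in the subject's best interest. That is a judgement, and it names pregnancy and new malignancy but not anaphylaxis.
- 12.5.1 applies only once a pausing criterion is met. It would apply if the investigator invoked the third criterion.
- 13.1 sends reportable events to the IRB under Policy 801. This route is separate, and its timelines are not given.

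None of these requires a hold before the next dose in this case.

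**Step 3: time to decide if a pause were mandatory.** Visits 6 and 7 are set at 28 ± 5 days, and Visit 8 and the later dosing visits at 28 ± 7 days (6.3.4 to 6.3.6, 6.4.2, 6.4.3). The places differ on the anchor. Those sections count from the prior dosing visit, while the notes to Table 1 in Appendix B say Visits 6, 7 and 8 are scheduled monthly from Visit 4.

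*Windows from the prior visit.* The latest in-window dose is 28 + 5 = 33 days after the previous one (doses 2 and 3), or 28 + 7 = 35 days (Visit 8 onward).

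*Windows from Visit 4, previous visit at its late limit.* Visit 6 falls on day 28 + 5 = 33 after Visit 4. The Visit 7 window closes on day 56 + 5 = 61, leaving 61 − 33 = 28 days. If Visit 7 falls on day 61, the Visit 8 window closes on day 84 + 7 = 91, leaving 91 − 61 = 30 days.

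For a reaction *d* days after a dose, the days left are the interval minus *d*:

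| Reaction on day *d* | From prior visit (33 − *d* / 35 − *d*) | From Visit 4, late case (28 − *d* / 30 − *d*) |
|---|---|---|
| 0 | 33 / 35 | 28 / 30 |
| 7 | 26 / 28 | 21 / 23 |
| 14 | 19 / 21 | 14 / 16 |
| 28 | 5 / 7 | 0 / 2 |

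Visits 9 to 13 run from the prior visit in both places, so 35 − *d* applies there throughout.

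**The case against.** The strongest reply is that the premise is not in the documents. Section 8.1.1 lists risks without calling them expected, and 12.2 leaves the classification to case-by-case judgement. A serious anaphylaxis judged unexpected already forces a pause and a report. This stands, and it makes the point conditional.

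The second reply is that the case is largely covered. The third criterion is broad, and invoking it brings the 12.5.1 report with it. The list of criteria is worded as inclusive rather than exhaustive. Best-interest withdrawal is available, and every dosing visit lists an AE assessment, so the investigator has a decision point before each dose. A competent investigator would probably hold the dose. All this is fair and shrinks the gap, but each route depends on discretion, which a mandatory trigger is meant to replace.

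The third reply is that a new trigger swaps one judgement for another, since relatedness and resumption also rest with the principal investigator. That is correct: the gain is a formal hold and a prompt report, not an independent check.

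A reader might also infer that one non-serious Grade 3 hypersensitivity reaction should force a pause. It meets neither event criterion, even if unexpected. However, the plan deliberately sets a two-event threshold for such events, and nothing in the documents shows that threshold to be wrong.

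**Conclusion.** The concern holds in conditional form. If the principal investigator classes a related anaphylaxis as expected, 12.5 mandates no hold before the next dose and 12.5.1 mandates no report; the pause then rests on judgement. The size is a matter of rule logic: 0 of 2 event-defined criteria are met. No frequency can be attached and no effect on an endpoint or analysis is claimed. This is a cheap safety improvement to a small, closely followed pilot.

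Two stronger readings are not supported. One is that the protocol treats anaphylaxis as expected, or permits re-dosing after it without review; no section says so. The other is that such an event would go unreported to the IRB. Reporting under Policy 801 runs separately, and its content cannot be judged from these documents.

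The conclusion assumes that the event is judged at least possibly related and that Policy 801 does not itself settle expectedness or impose a dose hold.

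**What to change.** Add one criterion to 12.5: *any anaphylaxis, or serious systemic hypersensitivity reaction, possibly, probably or definitely related to study agent, regardless of expectedness*. Section 12.5, unlike 12.6, has no closing sentence that leaves the measure itself to the principal investigator, so the added line would require both the hold and the 12.5.1 report.

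Leave the three existing criteria, the 12.5.1 report, the resumption decision in 12.5.2 and the halting rules in 12.6 unchanged. Do not add a trigger for a single non-serious Grade 3 reaction.

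The change needs one line and no new staff, committee or data. Its cost is an occasional extra pause, including for some events that are hard to tell from an EAE flare. The pause is reversible, but it may push a dose outside its window. That matters because the primary endpoint follows three doses in about 12 subjects. For reactions soon after dosing there are several weeks to decide under either reading of the windows. Only a reaction late in the interval is tight.
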